Phase II part 1: Evaluable patients' population for tumor response (evaluable per protocol population, EPP): consists of all included patients who were dosed with both IMPs (TG4001 + avelumab) and have at least one baseline and one post-baseline evaluable CT-scan at week 6 after start of study treatment with a best overall response assessment different from 'Unknown' according to RECIST 1.1 evaluation criteria. However, if a patient progressed or died due to underlying cancer before scheduled scan 6 weeks after study treatment start could be performed, the patient will still be included in the evaluable population. Any patient who has a major inclusion/exclusion violation, major dosing violation, or major protocol conduct violation will be excluded from the EPP. Major dosing violation is considered when minimum exposure is not met, defined as at least 6 TG4001 injections and 3 avelumab administrations except if patient has progressed or died due to underlying disease before or at the first evaluation. Due to potential abscopal effect when associating radiotherapy and immunotherapy, patients receiving palliative radiotherapy will be analyzed separately. Whatever the reason for withdrawal, except for disease progression and death due to underlying cancer before scheduled scan 6 weeks after study treatment start could be performed, patients considered as non-evaluable for tumor response will be replaced.

Descriptive statistics will be used. For all analyses, results and graphical representation of data will be presented by dose level and phase II cohort.

No statistical analyses will be performed on safety data. Safety summary tables will include all safety assessments up to 90 days after last study treatment administration.

Phase II part 2:

Full Analysis Set (FAS) will be the primary set for efficacy analyses. It consists of all randomized patients who were administered at least one dose of IMP(s) according to the treatment allocated at randomization.

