7.6. Safety follow-up phone call

At 90 days after the last administration of study treatment, patients will be contacted by telephone to collect information on new or ongoing SAEs and treatment-related non-serious AEs. Patients will also be asked about any further antineoplastic therapy.

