9.1. Definitions

Treatment Emergent Adverse Event (TEAE)

A treatment-emergent adverse event (TEAE) is defined as a sign or symptom that emerges during treatment or within 30 days of the last dose of the study drug, having been absent pre-treatment or that has worsened relative to the pre-treatment state. Any adverse event deemed

related to study drug will also be considered a TEAE regardless of elapsed time since last study drug dose.

Adverse Event (AE)

An AE for the purposes of this protocol is a medical occurrence or deterioration of a pre-existing medical condition occurring after signing the informed consent and even if the event is not considered to be related to the study treatment(s).

Preexisting medical conditions (other than the condition being studied) judged by the investigator to have worsened in severity or frequency or changed in character during the protocol-specified AE reporting period.

Adverse reaction (AR):

All noxious and unintended responses to a medicinal study product (TG4001 or avelumab) related to any dose or to a study specific procedure.

Laboratory abnormality

A laboratory abnormality is reported as an AE if it is out of range, considered by the Investigator as clinically significant (i.e. with clinical manifestations or requiring treatment or clinical management).

Other significant abnormalities

Any significant worsening noted during interim or final physical examinations, electrocardiograms, x-rays, and any other potential safety assessments, whether or not these procedures are required by the protocol, should also be recorded as a non serious or serious AE, as appropriate, and reported accordingly.

Other significant adverse events

Any events and any laboratory abnormalities that led to an intervention, including withdrawal / dose reduction of IMP or significant additional concomitant therapy other than those reported as SAE, and that are considered by Transgene or the Investigator to be of special interest because of clinical importance.

Serious Adverse Event (SAE) / Serious Adverse Reaction (SAR) / Suspected Unexpected Serious Adverse Reaction (SUSAR):

Any untoward medical occurrence that at any dose:

- results in death,
The death of a patient is not per se an AE but an outcome. “Death” should be considered as a SAE only in case of “unexplained death” when no cause is identified. The event that resulted in a fatal outcome should be determined and reported as the SAE.
- is life threatening,

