9.2. Time period for collection

The study period during which all Aes and SAEs must be reported begins after informed consent is obtained and ends 30 days following the last administration of any study treatment (safety follow up visit). If the safety follow-up visit is performed less than 30 days after the last IMP administration, any AE / SAE occurring between the safety follow-up visit until 30 days after last study treatment administration will be considered as AE / SAE and notified to Transgene, regardless of their relationship to IMP(s).

After this period, and until day 90 after last administration of study treatment (i.e. until safety follow-up phone call) investigators should report treatment-related non-serious AE and all SAEs. Ongoing SAEs at the 90-day safety follow-up phone call must be followed up until stabilization or until the outcome is known, unless the patient is documented as “lost to follow up”.

SAEs occurring more than 90 days after administration of the last dose of any study treatments, and evaluated by the investigator as related to the IMP(s) should be collected and reported to the sponsor indefinitely even after study closure. These will however not be reported in the eCRF after Database lock.

If an Adverse Event occurs during the screening period (i.e., after ICF signature and before start of study treatment), it will be recorded either on a “Medical history/ current conditions” page for an identified syndrome (e.g., pneumonia) or on a “Signs and symptoms” page for symptoms with no associated syndrome (e.g., diarrhoea).

From start of study treatment, AEs will be recorded on an “AE” page. In case of worsening of a medical condition which started before start of study treatment, an AE page will be completed using a verbatim starting by “worsening of...”.

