9.3.2. Follow-up

Once an AE is detected, it must be proactively followed until its resolution or 30 days after the last study treatment administration. After this visit and until day 90 after last administration of study treatment non-serious treatment-related Aes and all SAEs have to be followed. Ongoing SAEs at the 90-day safety follow-up phone call must be followed up until stabilization or until the outcome is known, unless the patient is documented as “lost to follow up”.

In addition, any significant AE as recommended by Transgene must be followed until it is resolved or stable or returned to baseline status.

Transgene or its representative reserves the right to ask for further information on any AE/SAE that may be considered of interest or when the event is not previously documented in the IB (new occurrence) and is thought to be related to the study treatment.

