10.4. Statistical and analytical plans

10.4.1. Safety analyses

All safety analyses will be performed and summarized in the SAF.

Adverse Events

AE summaries will include all AEs starting on or after start of study treatment or that has worsened on or after start of study treatment and starting no later than 90 days after the date of last study treatment administration.

All Aes, significant Aes, Aes leading to discontinuation of study treatment (overall and by component: TG4001, avelumab), severe Aes (Grade 3 or 4) and serious Aes (SAE) will be listed and summarized by System Organ Class (SOC) and Preferred Term (PT), intensity (based on the NCI CTCAE grades, also referred as CTCAE), relationship to study treatment (TG4001 and/or avelumab).

Separate AE summaries will be presented by SOC, PT, and CTCAE grade. In the summaries presented by grade, all Aes will be pooled. Specific tables will summarize related Aes to IMP and Aes of specific interest (injection site reactions).

The frequency of CTCAE Grade 3 and 4 Aes will be summarized separately.

Written narratives will be produced for all SAEs and unexpected or other significant Aes that are judged to be of special interest because of their clinical importance.

Adverse events/SAEs occurring after signing the Informed Consent Form (ICF) but before starting study treatment, including those observed in patients screened but not included will be listed separately from those occurring after treatment start.

Fatal Events

All fatal events will be listed and summarized by System Organ Class (SOC) and Preferred Term (PT). The nature of the event leading to death should be recorded. Sudden/unexplained death will be coded as “death”.

Fatal events will be summarized by presenting the number and percentage of patients who died. Data will be presented by SOC and PT using MedDRA coding.

Fatal events occurring after signing the Informed Consent Form (ICF) but before starting study treatment in patients screened but not included will be listed separately from those occurring after treatment start.

Laboratory abnormalities

The summaries will include all laboratory assessments collected no later than 30 days after treatment discontinuation. All laboratory assessments will be listed and those collected during 30 days after study treatment discontinuation will be flagged in the listings.

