j Tumor evaluation must be performed every 6 weeks for the first 9 months from treatment start and every 12 weeks thereafter, with a time window allowed of +/- 7 days.

k During the study, hematology and serum chemistry (and pregnancy test, if applicable) will be evaluated by local laboratories. The results of hematology and chemistry (and pregnancy test, if applicable) **must be reviewed before study treatment administration**. Local labs may be drawn up to 2 days before study treatment administration to meet this requirement.

l For women of childbearing potential

p Does not include blood collection for PBMC, blood collection is limited to 9 ml.

q Blood collection of 59 ml.

r For each patient, an end of treatment visit (EOT) will be scheduled once the patient is discontinued from all study treatments.

s Must occur 30 days after the last study treatment administration. All AEs and SAEs will be documented until this visit.

t Must occur 90 days after the last study treatment administration. Patients will be contacted by telephone to collect information on new or ongoing SAEs and treatment-related non-serious AEs. Any SAE assessed as related to IMPs must be reported whenever it occurs, irrespective of the time elapsed since the last administration of IMPs. Patients with an ongoing SAE at the 90-day Safety Follow-up Phone Call must be monitored and followed by the Investigator until stabilization or until the outcome is known, unless the subject is documented as “lost to follow-up”.

u Long-term follow-up for survival, every 3 months after the safety follow-up visit or last PFS follow-up visit (may be performed by phone contact).

v For patients with accessible lesions tumor sample on biopsy at the time of progressive disease

** Beyond 2 years of treatment and based on the clinical judgement of the investigator the patient could continue to receive study treatments.

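### The all-AE and by-grade tables run to 90 days after last dose, but unrelated non-serious AEs are collected only to day 30

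*Combined protocol and SAP*

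**What the plan says.** Section 10.4.1 defines the AE summaries by onset or worsening from the start of study treatment, "starting no later than 90 days after the date of last study treatment administration". It lists summaries of all AEs by system organ class, preferred term, intensity and relationship, and separate output for Grade 3 and 4 events, SAEs and related AEs. It sets no different rule for days 31-90. In the statistical methods part of the synopsis, "Safety summary tables will include all safety assessments up to 90 days after last study treatment administration".

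The collection rules are narrower. Section 9.2 requires all AEs and SAEs from consent to 30 days after the last dose. After that and up to day 90, "investigators should report treatment-related non-serious AE and all SAEs". Section 7.6 gives the same content for the 90-day call: "patients will be contacted by telephone to collect information on new or ongoing SAEs and treatment-related non-serious AEs". Section 9.3.2 says of the same period that "non-serious treatment-related Aes and all SAEs have to be followed". The phase II part 2 flow-chart (Appendix IIID) says of the 30-day visit: "All AEs and SAEs will be documented until this visit".

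Section 9.1 adds a third window. A TEAE is one that "emerges during treatment or within 30 days of the last dose of the study drug", or any event judged related, however late. Section 10.4.1 does not refer to this definition.

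**The concern.** An incidence table headed as all AEs to day 90 tells its reader that every AE with onset in that period had a chance to be counted. Under section 9.2 that is true only to day 30. Later, an event is requested only if it is serious or the investigator judges it related, so part of what the table claims to count is never asked for.

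Two things follow. Incidence of unrelated non-serious events is too low for the stated window. The proportion of AEs that are related or serious is too high, because the late part of the denominator has been filtered on those same attributes. Section 10.3.2 bases the safety assessment mainly on the frequency of AEs and SAEs, so these tables are the main descriptive safety output.

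**Working it through.** No sample size, power or event count enters this point, so the check sets the windows side by side.

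| Item | Source | Limit after last dose | Restriction |
|---|---|---|---|
| AE summaries | 10.4.1 | 90 days | none |
| Safety tables | Synopsis, statistical methods | 90 days | none |
| Full AE collection | 9.2; Appendix IIID footnote | 30 days | none |
| Late AE collection | 9.2, 7.6, 9.3.2 | days 31-90 | serious, or non-serious and related |
| TEAE definition | 9.1 | 30 days, plus related events at any time | mixed |
| Laboratory summaries | 10.4.1 | 30 days | none |

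**Length of the filtered period.** 90 - 30 = 60 days, and 60/90 = two thirds of the post-treatment window. The first 30 days are complete by design: section 9.2 requires AEs up to day 30 regardless of relationship even when the safety visit takes place early.

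**Direction of the effect.** Let R be related AEs, S unrelated SAEs and U unrelated non-serious AEs. Subscript 1 is onset up to day 30 and subscript 2 is onset on days 31-90.

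- Requested: R1 + S1 + U1 + R2 + S2.
- Implied by the table's definition: R1 + S1 + U1 + R2 + S2 + U2.
- Shortfall: U2, all unrelated and non-serious.
- Share related as tabulated: (R1 + R2) / (R1 + S1 + U1 + R2 + S2). The complete share has the same numerator and a denominator larger by U2. The tabulated share is therefore never lower than the complete one, and is higher whenever U2 > 0. The same holds for the share that is serious.

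The documents give no value for U2, so the size of the shortfall cannot be computed.

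**Which tables are affected.**

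- All AEs by system organ class and preferred term: affected through U2.
- AEs by CTCAE grade, and the Grade 3 tables: affected for unrelated non-serious events.
- Clinical Grade 4 events: not affected, because section 9.6 requires them to be reported as SAEs.
- SAE tables and related-AE tables: not affected, because both classes are collected to day 90.

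**Reconciling text.** None was found. The protocol refers to a separate statistical analysis plan for the adaptive method (10.2), laboratory shift tables (10.4.1) and protocol deviations (10.6). None of these references concerns the AE window.

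**The case against.** The strongest reply is that this is an ordinary convention, openly described. The TEAE definition itself joins a complete 30-day window to an extension for related events, and what would appear in the tables is close to that set plus late unrelated SAEs. On this view the 90 days is only an onset cut-off for whatever was recorded. The SAE and related-AE tables that hold the important late events are already planned, and a shorter main window would take delayed immune-related events out of it.

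Part of this stands. The gap is confined to late unrelated non-serious events, and the protocol states its collection rule plainly. Keeping late related events visible is a sound aim, and the fix has to respect it. But reading the cut-off as applying to recorded AEs does not make an all-AE incidence to day 90 interpretable. Section 10.4.1 neither invokes the TEAE definition nor states the filter.

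The synopsis is weaker support than section 10.4.1. Its 90-day sentence comes before the phase II part 2 heading and may describe only the single-arm parts.

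A reader might go further and infer that the comparison between arms is biased: part 2 is open label, relatedness is the investigator's judgement, and a combination patient has two products to which an event can be attributed. That is possible, but the documents neither show nor quantify it. Both arms receive avelumab, relationship is recorded separately for each product, and section 10.4.1 specifies no between-arm safety test. Two-product attribution would also affect related-AE tables at every time point, whatever the window. Nor does comparing the 60 days with the assumed 2.0-month control median PFS measure any bias. PFS runs from randomisation, controls start dosing a week later, and part 2 allows treatment beyond first progression.

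**Conclusion.** The point holds as a minor inconsistency in descriptive safety tables. Section 10.4.1, and the synopsis where it applies, claim a 90-day window for all AEs that the collection rules fill completely only to day 30. For the remaining 60 days the all-AE, by-grade and Grade 3 tables omit unrelated non-serious events, and the share of related or serious events is raised to an unknown extent.

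This rests on two assumptions: that sites collect what section 9.2 asks for and no more, and that no separate analysis plan redefines the window. Such a plan was not available to check; even if it does so, section 10.4.1 would still need correcting. The documents do not support a claim of demonstrated bias between arms, or of any effect on the primary PFS analysis.

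**What to change.** In section 10.4.1, and in the synopsis sentence:

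1. Base the all-AE and by-grade incidence tables, including Grade 3, on onset or worsening from first dose to 30 days after last dose. State this lower limit explicitly, because the definitions table equates start of study treatment with randomisation in part 2.
2. Keep the planned SAE and related-AE tables to day 90, and show onset on days 31-90 separately so that late immune-related events stay visible.
3. State how these tables relate to the TEAE definition in section 9.1. Adopting that definition unchanged would not remove the mix, since it adds related events at any time.

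The cost is a text edit, one programming window and one or two extra tables. Collection, site workload and the data held do not change. The downside is that late related events and SAEs leave the main all-AE table and must be read from the separate tables. A footnote describing the filter would be cheaper, but would leave the 90-day incidence incomplete. The window should be settled in writing before the final analysis, so that it is not chosen with the data in view.

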7.7. Post-study follow-up

PFS-FU visit:

For patients who stopped the study treatment for a reason other than progressive disease based on RECIST 1.1 (e.g., AE), tumor evaluation should be obtained every 6 weeks until disease progression by RECIST 1.1 or for a period of 9 months after the start of study treatment. Beyond 9 months, the evaluations will be performed every 12 weeks until disease progression by RECIST 1.1. Tumor measurements will be recorded in the eCRF with the date and method of tumor assessment and the response evaluation in PFS-FU visit. This follow-up should be done even if patients start subsequent antineoplastic therapies.

Further antineoplastic therapies, given after end of study treatment will be reported in the eCRF with the start date and end date.

Tumor sample on biopsy at the time of progressive disease is to be performed for phase II part 2 in patients with accessible lesions at the time of progressive disease.

OS-FU:

From the safety follow-up or last PFS follow-up visit the patient will be followed for survival every 3 months until death (phone call is considered as a follow-up) or until the date of last contact if the patient is lost to follow-up or withdraws consent for collection of long-term data.

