9.4. Reporting of DLTs during the phase Ib of the study

During the phase Ib of the study, Transgene must be informed **immediately by the center** of the occurrence of any DLT occurring within the first 4 weeks of study treatments in all patients included in the phase Ib of the study.

The following action must be undertaken by the investigators on occurrence of any AE that fulfill the criteria for a DLT:

- The Investigator must inform Transgene and duly complete the appropriate eCRF form even if the data are incomplete or if it is obvious that more data will be needed.
- The following information must be present: description of the AE, intensity and relationship to study drugs, date of onset, status at the time of reporting, action taken on study treatments.
- Transgene may request any additional information (copies of reports, lab tests etc.,) to the center in order to better assess the DLT.

9.5. Serious Adverse Event / Serious Adverse Reaction / Suspected Unexpected Serious Adverse Reaction notification

Reporting to Transgene

Any SAE occurring during the course of the study (from the signature of ICF and up to 90 days after last study treatment administration whether or not related to the IMP(s) MUST be reported to Transgene. The Investigator must complete and fax a “Serious Adverse Event Form” to Transgene within a maximum of 24 hours of occurrence or knowledge of the event.

France	
Pharmacovigilance Physician	
[REDACTED]	[REDACTED]

An Investigator designee may complete the SAE form, however, the Investigator must sign it. The form can be sent to Transgene with the designee's signature if the Investigator's signature

cannot be obtained within one working day. The Investigator's signature must be obtained as soon as possible, as well as his/her evaluation of the relationship to the IMP(s). The signed form must be faxed to Transgene immediately.

The SAE form should be completed in English.

Follow-up information (e.g., complications or progression of the initial SAE) must be notified to Transgene by the Investigator within the same time frame as the initial SAE form by using a new "SAE form" with the box "follow-up" ticked and sent to Transgene. The follow-up information should describe whether the event has resolved or continues, if and how it was treated and whether the patient continued or withdrew his/her consent.

Transgene or its representative may request further information as needed.

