Phase II part 2: The primary endpoint of phase II part 2 is PFS by RECIST 1.1 criteria. The FAS will be the primary population for efficacy analyses in the phase II part 2. These analyses will be repeated on the EPP.

Progression Free Survival (PFS) is defined as the time from the date of randomization to the date of first documented tumor progression or death due to any cause, whichever occurs first. If a patient has not had a PFS event at the cut-off date for analysis or at the date when a further antineoplastic therapy (other than those planned as study treatment in the protocol) is started, PFS will be censored at the date of last evaluable tumor assessment before the cut-off or start of further antineoplastic therapy.

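### AE and SAE summaries run to 90 days after last dose with no stop or flag at the start of the next cancer therapy, so SAEs to day 90 and AEs to day 30 can include that therapy's toxicity

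*Combined protocol and SAP*

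**What the plan says.** Section 10.4.1 (Adverse Events) includes events from the start of study treatment and "starting no later than 90 days after the date of last study treatment administration". The synopsis, under Statistical Methods, agrees: "Safety summary tables will include all safety assessments up to 90 days after last study treatment administration". Neither place mentions next-line therapy.

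Collection is narrower than the summary window. Under Section 9.2, AEs of any cause are collected to day 30 after the last dose. From then to day 90, "investigators should report treatment-related non-serious AE and all SAEs". Section 9.5 confirms that SAEs "up to 90 days after last study treatment administration whether or not related to the IMP(s) MUST be reported to Transgene". Section 9.6 makes every clinical Grade 4 event an SAE.

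Two other safety windows are shorter. Section 9.1 defines a treatment-emergent event as one that "emerges during treatment or within 30 days of the last dose of the study drug", extended only for related events. The laboratory summaries in Section 10.4.1 also stop at 30 days.

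The date of next-line therapy is held. Section 7.7 says: "Further antineoplastic therapies, given after end of study treatment will be reported in the eCRF with the start date and end date". The efficacy analysis uses it. In Section 10.3.1, "PFS will be censored at the date of last evaluable tumor assessment before the cut-off or start of further antineoplastic therapy", and Section 10.3.2 treats duration of response the same way.

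**The concern.** Progression is a main reason for stopping study treatment, and Section 6.9 places no limit on what patients may receive afterwards. The protocol expects next-line therapy inside the 90 days: it asks about it at the end-of-treatment visit, the 30-day visit and the 90-day call, which is also when SAEs are collected. An SAE caused by that therapy on, say, day 60 falls in the window and would be counted in the all-cause SAE table of the patient's study arm.

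Safety is a secondary objective in phase II, and Section 10.3.2 bases it largely on AE and SAE frequencies. Part 2 is the only randomised view of what TG4001 adds to avelumab. A table that mixes in another drug's events is harder to read for either arm. If one arm stops treatment sooner, the share of its safety time exposed to the next drug also differs.

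**Working it through.** The plan gives no figure on this point, so there is none to reproduce. The check has four parts.

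**1. Which next-line events can reach the tables**

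| Event | To day 30 after last dose | Days 31-90 |
|---|---|---|
| SAE, any cause | collected and summarised | collected and summarised |
| Non-serious AE judged related | collected and summarised | collected and summarised |
| Non-serious AE judged unrelated | collected and summarised | not collected |

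The gap therefore affects all AEs to day 30 and SAEs to day 90, including serious Grade 3-4 events. It hardly touches non-serious AEs after day 30.

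**2. Share of safety time on next therapy, complete follow-up**

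Inputs from the plan: median PFS 2.0 months (control) and 4.5 months (combination), and the 90-day window. Assumptions: exponential times, last dose at progression, and next therapy starting d days after last dose. The documents give no value for d.

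- Mean time on treatment = median / ln 2: 2.0/0.693 = 2.885 months; 4.5/0.693 = 6.492 months.
- Window after last dose: 90/30.44 = 2.957 months.
- Total safety time: 2.885 + 2.957 = 5.842; 6.492 + 2.957 = 9.449 months.
- Share on next therapy = [(90 - d)/30.44] / total.

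| d (days) | Months on next therapy | Control | Combination |
|---|---|---|---|
| 14 | 2.497 | 43% | 26% |
| 28 | 2.037 | 35% | 22% |
| 30 | 1.971 | 34% | 21% |
| 42 | 1.577 | 27% | 17% |

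These shares apply to patients who receive next therapy. If 50-80% receive it (assumption), the d = 28 averages over all patients are 0.349 × 0.5 to 0.349 × 0.8 = 17-28% for control and 0.216 × 0.5 to 0.216 × 0.8 = 11-17% for the combination.

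**3. Allowing for data cut-off**

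A simulation used the same medians, 80 patients, uniform accrual and last dose at progression. It took accrual of 3 per month with cut-off at month 27 or 30, or 2 per month with cut-off at month 40 or 43 (cut-offs assumed).

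- The period after last dose is 49-50% of control safety time and 30-31% of combination safety time.
- If all patients start next therapy at day 30, it covers 32-33% and 19-20%; at day 60, 16% and 9-10%.
- Patients off treatment at cut-off: about 90-97% and 77-90%, a gap of 8-13 points that narrows as follow-up matures.

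The planned tables count patients, and each patient who stops has one window of the same length. The last line is therefore closer to the effect on those tables than the time shares are.

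**4. Whether truncating the counts is enough**

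Suppose the true SAE hazard before next therapy is 0.05 per month in both arms (assumption), 50-80% start next therapy at day 28 (0.920 months), and counting stops there.

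- P(no SAE on treatment) = 1/(1 + 0.05 × mean): 0.874 control, 0.755 combination.
- P(no SAE in the remaining window), with exp(-0.05 × 0.920) = 0.955 and exp(-0.05 × 2.957) = 0.863: 0.5 × 0.955 + 0.5 × 0.863 = 0.909; 0.8 × 0.955 + 0.2 × 0.863 = 0.937.
- P(at least one SAE), 50% uptake: control 1 - 0.874 × 0.909 = 0.206; combination 1 - 0.755 × 0.909 = 0.314; ratio 1.5.
- At 80% uptake: 0.181 and 0.293; ratio 1.6.

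The crude truncated ratio is 1.5-1.6 with no true difference, because combination patients are observed longer. The rate per patient-month is 0.05 in both arms, ratio 1.0. Truncation needs exposure-adjusted rates beside it.

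**The case against.** Much is already in place. Tables are split by relationship to TG4001 and avelumab, all SAEs get narratives, and the definition of an unrelated event in Section 9.3.1 allows for other therapies as the cause. This stands as partial mitigation. It depends on investigator attribution in an open-label trial, and it does not clean the all-cause SAE and Grade 3-4 tables.

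A long window also has a purpose, since immune-related reactions can appear late, and censoring PFS at next therapy does not oblige the safety analysis to do the same. That is fair. It argues for keeping collection to day 90 and keeping related events in the main table, not for leaving next-line events unmarked.

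A reader might infer that all AE tables are contaminated to day 90. The collection rule in Section 9.2 rules that out for non-serious events after day 30.

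A reader might also infer that control-arm SAEs are inflated enough to hide excess toxicity of the combination. The documents do not support this. They give no SAE rates, no lag to next therapy and no uptake, so any risk ratio would rest on invented hazards. With one such set (per month: avelumab 0.05, combination 0.10, off drug 0.05, next therapy 0.10), about 60-65% of the fall in the risk ratio remains when next therapy is given the off-drug hazard. Most of that fall comes from window length. The risk difference moves only from 24-25 to 21-22 points. Part 2 also allows dosing beyond first progression, and patients whose PFS event is death receive no next therapy. Both weaken the arm contrast. No formal between-arm safety test is planned.

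**Conclusion.** The gap is real and limited. As written, the all-cause SAE summaries to day 90, including serious Grade 3-4 events, and the all-cause AE summaries to day 30 can include toxicity of a later treatment, and nothing in Section 10.4.1 separates it.

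Among patients who receive next therapy about 28-30 days after last dose, it would cover roughly a third of control safety time and a fifth of combination safety time. The direction follows from the planned medians. The size rests on exponential times, last dose at progression and an assumed lag. The documents do not themselves say that the control arm is more affected, and the effect on patient counts is modest.

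Alpha, power, sample size and the PFS analysis are untouched. The change is still worth making before the final analysis, because it needs no new data and loses no event.

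**What to change.** Leave collection and reporting to day 90 unchanged. In Section 10.4.1 and the matching synopsis sentence:

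- End the main all-cause AE, Grade 3-4 and SAE summaries at the earlier of 90 days after last dose and the day before the first further antineoplastic therapy.
- Keep events judged related to TG4001 or avelumab in the main summaries for the full 90 days.
- Put the remaining events in a separate table by arm, headed 'after start of further antineoplastic therapy'.
- Give SAE rates per patient-month over the same windows, because observation time differs by arm.

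The cost is a wording change, one derived date from data already in the eCRF, and one extra table. The downside is that a delayed immune-related event wrongly blamed on the next therapy would appear in the second table and not the main one. It would still be reported, and the SAE narratives give a place to check it.
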